The allocation will be unblinded to investigators and participants. We plan to over-sample the glomerular cohort B and limit enrollment of the non-glomerular cohort A to ensure adequate distribution of the sample by disease etiology in a proportion generalizable to the national pediatric CKD population (2:1). The proposed allocation distribution is detailed in Section 1.3 and Table 2.

Hyperuricemia is defined in this protocol as having at least two measures of serum UA ≥ 5.5 mg/dL in the last 12 months, or actively treated with a XO inhibitor for a previous diagnosis of hyperuricemia. Participants actively treated with a UA lowering agent (Allopurinol, Febuxostat, or Losartan) will undergo a washout period of a minimum of 1 month (up to 3 months) prior to enrollment in the trial, then randomized to treatment versus control groups. None of the patients in the CHoR Pediatric Nephrology group practice actively treated with these agents had/have symptomatic hyperuricemia, and only 3 out of 14 treated have reached the target UA level of 3-5 mg/dL which will be applied in this study protocol. As it is unknown to what degree patients are benefiting from a minimal reduction of UA but with a persistent hyperuricemia, the CHoR Pediatric Nephrology Division has concluded that it is ethical for consenting participants actively receiving a XO inhibitor to be randomly assigned to treatment or control after a wash-out period.

Allopurinol dose will be initiated using standard weight-based dosing at the Baseline Visit 1 (V1), and titrated at Visits 1A and 2 (V1A, V2) to achieve a goal UA level in the normal range of 3-5 mg/dL by Visit 3 (V3).

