At baseline, demographic and anthropometric data, CKD disease etiology and duration since diagnosis, current medications, and presence of proteinuria or hypertension will be collected. At baseline and 6 months, casual clinic BP will be obtained (the average of three measurements) for hypertension assessment. Serum and non-invasively obtained urine will be collected at baseline, 3, and 6 months for basic or comprehensive metabolic panel, UA, cystatin C and creatinine-based GFR measurements. An additional serum and urine sample for purposes of dose titration and safety will be collected from the treatment group but not control at Visit V1A. The residual serum and urine samples will be bio-banked for the analyses of Aim 2. Adverse events will be collected and adherence will be measured at the V1A, V2, and V3 visits by pill count and through a validated visual analogue scale of adherence [26]. Participants will also receive a one-time monetary compensation at the conclusion of the study (V3).

Table 1. Study Timeline and Data Collection

Study Visit	Subject identification	Baseline Visit (V1)	Visit 1A (V1A)	Visit 2 (V2)	Endpoint Visit (V3)
Time	-1 to -3 months	0	+1 month	+3 months	+6 months
Encounter Purpose	1-3 month Allopurinol washout	Study enrollment, Randomization, baseline values	UA titration, Adherence & Safety check	UA titration, Adherence & Safety check	Study endpoint
Data Collection of Treatment group	C, G	A-E, G	D, F	C, E, F	A-F
Data Collection of Control group	C	A-E	No visit	C	A-E
Data Collection key	A: Demographic, anthropometric, medication history, clinic BP B: Vital signs including 3 casual clinic BP measurements C: Standard of care lab work: Serum – Basic metabolic panel, UA, cystatin C; Urine – Protein, creatinine, UA D: Serum Comprehensive metabolic panel; urine UA, creatinine. E: Reserve residual serum and urine samples for biomarker analysis F: Pill count, Adherence visual analogue scale, Evaluation of adverse events G: Urine pregnancy test if applicable to females of reproductive age				

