This randomized controlled trial aims to test the hypotheses that treatment of hyperuricemia with a xanthine oxidase inhibitor (Allopurinol) reduces the rate of decline of kidney function in chronic kidney disease, and markers of renal injury and inflammation. The Data and Safety Monitoring Plan (DSMP) is outlined below. During this study, all data collected will be kept confidential in an encrypted database using identification codes. Only approved research team members will have access to the database. The study staff will review all data collection forms on an ongoing basis for data completeness and accuracy as well as protocol compliance. Reviews of subject accrual, including compliance with protocol enrollment criteria and adherence data, will be performed by the PI and study staff on a monthly basis.

Data on adherence to the treatment protocol will be collected on an ongoing basis by research staff and reviewed quarterly by the PI. Adherence of participants will be evaluated by performing pill counts at study visits and by a validated visual analogue scale of adherence (patient self-report) at the end of study visit. An intention to treat protocol is applied to this study. However, if adherence falls below a rate of 75% which might inhibit the ability of the study to test its primary hypotheses, the study investigators and statistician will convene to discuss methods for improving adherence.

The PI will designate an Independent Monitor to perform an independent review of ongoing study progress and safety. The Independent Monitor will not be a part of the key research personnel, and will be qualified to review the patient safety data. Progress reports, including patient recruitment, retention/attrition of the study as a whole as well as retention of subjects undergoing washout or conversion therapy to study initiation, and adverse events (AE), will be provided to the Independent Monitor every 6 months. The reports will be generated only from aggregate for the entire study population. A closed safety report with masked group assignment will be generated for the Independent Monitor by an unmasked member of the study team (research coordinator).

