An Annual Report will also be compiled and will include a list and summary of AEs. In addition, the Annual Report will address (1) whether AE rates are consistent with pre-study assumptions; (2) reason for dropouts from the study; (3) whether all participants met entry criteria; (4) whether continuation of the study is justified on the basis that additional data are needed to accomplish the stated aims of the study; and (5) conditions

whereby the study might be terminated prematurely. The Annual Report will be sent to the Independent Monitor and will be forwarded to the IRB.

AE reports and annual summaries will not include identifiable material. Each report will refer only to the subjects' identification code. An AE is any untoward medical occurrence in a subject during participation in the clinical study or with use of the intervention agent being studied. An adverse finding can include a sign, symptom, abnormal assessment (laboratory test value, vital signs, skin reaction or physical exam finding), or any combination of these. A serious adverse event (SAE) is any adverse event that results in one or more of the following outcomes:

- Death
- A life-threatening event
- Inpatient hospitalization or prolongation of existing hospitalization
- A persistent or significant disability/incapacity
- A congenital anomaly or birth defect
- An important medical event based upon appropriate medical judgment

AEs will be labeled according to severity, which is based on their impact on the patient. An AE will be termed "mild" if it does not have a major impact on the patient, "moderate" if it causes the patient some minor inconvenience, and "severe" if it causes a substantial disruption to the patient's well-being. AEs will also be categorized according to the likelihood that they are related to the study intervention and labeled: definitely unrelated, definitely related, probably related, or possibly related to the study intervention. AEs will be reviewed with participants at each study visit.

Occasional 1-10% mild AEs are mild nausea, mild elevation in liver transaminase levels, and are not expected to impact a patient. These risks are considered minimal and will be addressed in the protocol and consent form.

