The rate of moderate AEs is expected to be <1%. The protocol includes measures to reduce the risk of moderate to severe AEs. Moderate AEs include skin reaction, gastrointestinal distress, moderate elevation in liver transaminases. Subjects will be encouraged to report these occurrences at any time during the intervention period by telephone within 24 hours of experiencing an event. Any adverse event rate over 5% in 12 months will be reported to the IRB.

Severe AEs include skin reaction as with development of Stevens-Johnson syndrome, or a significant elevation in liver transaminase levels that require hospitalization, and will be reported immediately to the IRB if this occurs. SAEs that are unanticipated, serious, and possibly related to the study intervention will be reported to the Independent Monitor and IRB in accordance with requirements. The Independent Monitor will be a clinician appointed by the PI who is not involved with the study design or analysis and is not a study investigator.

Unexpected fatal or life-threatening AEs related to the intervention will be reported to the IRB within 7 days. Other serious and unexpected AEs related to the intervention will be reported to the IRB within 15 days. Anticipated or unrelated SAEs will be handled in a less urgent manner but will be reported to the Independent Monitor and IRB. In the annual AE summary, the Independent Monitor Report will state that they have reviewed all AE reports.

The study staff, PI, and Independent Monitor will review the conglomerate adverse event rates every 6 months. Review of AE and SAE reports will also occur on an ongoing basis by the PI and study staff.

This study will be stopped prior to its completion if: (1) the intervention is associated with adverse effects that call into question the safety of the intervention; (2) difficulty in study recruitment or retention will significantly impact the ability to evaluate the study endpoints; (3) any new information becomes available during the trial that necessitates stopping the trial; or (4) other situations occur that might warrant stopping the trial.

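### Table 1 schedules adverse-event evaluation for the Allopurinol arm only, while section 1.2 and the Data and Safety Monitoring Plan make no such restriction

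*Combined protocol and SAP*

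**What the plan says.** Three places in the combined protocol and SAP set out when AEs are collected.

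- Section 1.2 (Experimental Design): "Adverse events will be collected and adherence will be measured at the V1A, V2, and V3 visits". V1 is not listed, and neither arm is singled out.
- Table 1 (Study Timeline and Data Collection): AE evaluation exists only inside one code, "F: Pill count, Adherence visual analogue scale, Evaluation of adverse events". The treatment row carries F at V1A, V2 and V3. The control row reads C at identification, A-E at V1, no visit at V1A, C at V2 and A-E at V3, so F never appears.
- Data and Safety Monitoring Plan: "AEs will be reviewed with participants at each study visit". The AE definition in the same section covers any subject taking part, not only those on the study drug.

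Two design features bear on this. On blinding, section 1.2 states: "The allocation will be unblinded to investigators and participants". On oversight, the monitoring plan states: "A closed safety report with masked group assignment will be generated for the Independent Monitor".

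**The concern.** Table 1 is the visit-by-visit schedule that site staff are likely to work from. Followed literally, it has treated participants asked about AEs three times and controls never. Active questioning generally brings out complaints that people do not volunteer. A higher AE count in the Allopurinol group would then be a mixture of drug effect and unequal asking, with no means of separating the two. Open allocation adds to this, because staff and families know who is on the drug.

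The control arm is not free of study-driven treatment. About a quarter of participants are expected to be converted to Candesartan, which the investigational pharmacy supplies, and that includes controls. Their Table 1 row has no AE evaluation either.

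A secondary gap is V1. Allopurinol starts there, yet neither row has F at that visit. A complaint already present could first be written down at V1A, on treatment. This matters mainly for participants arriving from washout or Candesartan conversion.

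**Working it through.** The plan gives no figure to reproduce here. The check is a tally of scheduled AE evaluations under each of the three rules.

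Inputs: 28 Allopurinol and 14 control participants (Table 2); visit codes from Table 1; controls have no V1A visit (Table 1); about 1/4 of participants converted to Candesartan (Study Intervention Administration). For the monitoring plan's rule, I count V1, V1A, V2 and V3 as study visits and leave out the identification contact.

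AE evaluation scheduled, by visit:

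| Rule | Treated | Control |
|---|---|---|
| Table 1 | V1A, V2, V3 | none |
| Section 1.2 | V1A, V2, V3 | V2, V3 |
| Monitoring plan | V1, V1A, V2, V3 | V1, V2, V3 |

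Evaluations = participants × scheduled visits:

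- Table 1: 28 × 3 = 84 treated; 14 × 0 = 0 control; total 84.
- Section 1.2: 28 × 3 = 84 treated; 14 × 2 = 28 control; total 112.
- Monitoring plan: 28 × 4 = 112 treated; 14 × 3 = 42 control; total 154.

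Section 1.2 and the monitoring plan differ only at V1: 154 − 112 = 42, one evaluation for each of the 42 participants. Table 1 differs from section 1.2 only in the control row at V2 and V3: 112 − 84 = 28. The control gap therefore comes from the table, not from the text.

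Controls on study-supplied Candesartan: 14 × 1/4 = 3.5, so 3 to 4 of 14, assuming the quarter applies equally to both arms.

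A possible cause is that code F bundles AE evaluation with the pill count and adherence scale. Those two have no use in untreated controls, so leaving F out of their row would drop AE evaluation as well. This is inference; the plan does not say so.

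**The case against.** The strongest reply is that the text already settles the matter. Section 1.2 and the monitoring plan both cover controls at V2 and V3, and harm arises only if staff follow a table cell over two sentences. That stands as a limit: the consequence is conditional. It does not remove the conflict, because the plan states no order of precedence and the table is the working schedule.

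Existing safeguards also count. Code D gives both arms a comprehensive metabolic panel at V1 and V3, and elevated baseline liver tests are an exclusion, so raised transaminases have a pre-dose baseline and control data. BP is checked after Candesartan conversion, and conversion side effects and withdrawals must be reported. Participants are encouraged to telephone about moderate AEs within 24 hours. These cover laboratory, BP and volunteered events. None is a scheduled inquiry about AEs in controls.

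The V1 gap is the weaker part. Roughly three quarters of participants have no Candesartan conversion and, unless they are in washout, no study-driven exposure before V1.

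A reader might infer more than the documents support:

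- *That the V2 column heading itself shows the conflict.* The heading "UA titration, Adherence & Safety check" also stands over V1A, where controls have no visit. Titration and adherence checks concern treated participants only, so the heading is best read as describing that arm.
- *That uneven collection would unmask the Monitor's report.* With a 28:14 allocation, group sizes, if shown, would already reveal which group is which.
- *That the IRB trigger would be missed.* The rule is "Any adverse event rate over 5% in 12 months will be reported to the IRB", with no denominator. Pooling over 42 instead of 28 changes the answer only at exactly two treated participants with an AE: 2/28 = 7.1% against 2/42 = 4.8%. One is below 5% either way (3.6%, 2.4%), and three are above either way (10.7%, 7.1%). The sentence "The reports will be generated only from aggregate for the entire study population" concerns the Monitor's progress reports and does not set the trigger's denominator.
- *That a planned safety comparison is invalid.* No formal between-arm AE analysis is specified; the named outcomes are GFR, UA and BP, with biomarkers as exploratory.

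**Conclusion.** The inconsistency is real and minor. Table 1 schedules 84 AE evaluations for the treatment arm and none for controls. The text calls for 28 control evaluations (section 1.2) or 42 (monitoring plan). If Table 1 is followed, AE ascertainment is one-sided in an open-label trial, and any group difference in the masked-group safety report partly reflects who was asked. The 3 to 4 controls expected on study-supplied Candesartan would be among those not asked.

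This rests on three assumptions: full enrollment as in Table 2, staff following the table where it differs from the text, and a masked-group report that tabulates AEs by group. The table tally is certain; the size of any distortion in AE counts is unknown and cannot be derived from the documents. No GFR, UA or BP analysis is touched.

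**What to change.** Split code F in Table 1 into F1 (pill count and adherence scale, treatment row only) and F2 (AE evaluation). Put F2 at V1A, V2 and V3 in the treatment row and at V2 and V3 in the control row, and record onset dates. To match the monitoring plan, also put F2 at V1 in both rows, before the first Allopurinol dose. Reword the section 1.2 sentence to say that AEs are collected in both arms at every study visit from V1. Controls need no V1A visit.

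The cost is a wording amendment plus a few minutes per evaluation at visits that already take place. Added evaluations depend on the rule taken as current:

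- against the monitoring plan, 154 − 154 = 0;
- against section 1.2, 154 − 112 = 42;
- against Table 1, 154 − 84 = 70 (28 treated at V1, and 14 × 3 = 42 control).

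Treated participants will still have one more post-baseline evaluation than controls (three against two). Onset dates let a reader of the safety report allow for that without a new formal analysis.

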Aim 1. To determine the effect of Allopurinol treatment on GFR of hyperuricemic pediatric CKD patients. In a randomized controlled study, pediatric CKD patients with hyperuricemia (serum UA ≥ 5.5 mg/dL) will be allocated 2:1 to Allopurinol versus standard of care (SOC) control for 6 months. Participants will be stratified into two cohorts by disease etiology (cohort A: non-glomerular, cohort B: glomerular). Equal allocation of race is expected as our local population is composed of 50% black race. The primary outcome measure is the amount of GFR change from baseline to 6 months compared to the control group in both cohorts. Secondary outcomes are measurement of the amount of UA and BP change from baseline to 6 months.

Aim 2. Establish whether Allopurinol treatment reduces Nlrp3 inflammasome and renal injury biomarkers. In this exploratory aim, urine and serum biomarkers of Nlrp3 inflammasome activation (hs-CRP, XO enzyme activity, Nlrp3, IL-1 β , IL-18) and renal injury (KIM-1, ET-1, NAG, and NGAL) will be collected at 3 and 6 months and compared to baseline of cohorts A and B treatment and control groups.

Impact: GFR change from baseline to 6 months by treatment and cohort will be used to directly inform the effect size and sample size calculations required for a randomized controlled multicenter pediatric intervention trial. The simultaneous and novel exploration of the effect of XO inhibition on inflammation and renal injury biomarkers will provide crucial data that may identify mechanism of the XO inhibition effect.

BACKGROUND AND SIGNIFICANCE

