1.3. Statistical Analysis: We will report means/medians and standard deviations (SD)/interquartile range (IQR) for all continuous measures, and frequency and proportions for categorical variables. Assuming a clinically significant difference between treatment groups of 3 ml/min/1.73m² and individual group SDs=3.5, a one-sided analysis t-test performed at $\alpha=0.05$ will achieve at least 80% power for a sample size of 42 if the participants will be allocated in a 2:1 ratio between treatment and control. We will also enroll participants into two cohorts to assure proportional distribution between non-glomerular (cohort A) and glomerular (cohort B) disease etiology. Our local pediatric CKD population composition by disease etiology is similar to national proportions of approximately 70% non-glomerular and 30% glomerular disease etiology. We will therefore over-sample the glomerular sub-population in cohort B and limit enrollment of the non-glomerular cohort A to n=19, maintaining roughly a 2:1 proportion. The goal allocation enrollment by treatment group and cohort size is summarized in **Table 2**. Two-sample t-tests on the GFR change score will be used to address Specific Aim 1A while separate 2-way ANOVA models with an interaction will be used to address Aim 1B. Repeated measures ANOVA models will be used to inform from all three time points in an intent-to-treat fashion.

Table 2: Goal allocation enrollment

Treatment Group	Allopurinol Group	Control Standard of Care Group
Cohort A: Non-glomerular disease etiology	19	7
Cohort B: Glomerular disease etiology	9	7
Total	28	14

Specific Aim 2. Determine the effect of Allopurinol treatment on Nlrp3 inflammasome and renal injury biomarkers.

2.1. Rationale and Objective: To our knowledge there are no studies that explore the effect of XO inhibition on the known mechanism of hyperuricemia induced Nlrp3 inflammasome activation and renal injury in a clinical trial setting. We therefore propose to establish whether XO inhibition reduces levels of these biomarkers at 3 and 6 months compared to baseline. If our hypothesis is correct that inflammasome-mediated renal injury is improved by Allopurinol, we expect to find that after 3 and 6 months of Allopurinol treatment, the biomarker levels will be reduced from baseline in both treated cohort groups compared to control participants.

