2.2. Experimental Design: The study design of Aim 2 is the same as Aim 1 (see **Table 2**). We will measure the following biomarkers from reserved serum and urine samples at the baseline, 3, and 6 month visits. Activity of the Nlrp3 inflammasome will be measured via: serum high sensitivity CRP, Xanthine Oxidase

activity level, Nlrp3, Interleukins 1 β and 18, and urine Nlrp3 and IL-18. Renal injury biomarkers will be measured from serum NGAL, urine NGAL, NAG, KIM-1, and ET-1.

2.3. Statistical Analysis: We will report means/medians and standard deviations (SD)/interquartile range (IQR) for all continuous measures. Similar analyses will be used for Specific Aim 2 as Specific Aim 1. All sample size calculations were performed with nQuery Advisor v.7.0.

STUDY INTERVENTION ADMINISTRATION

The proposed intervention uses a study drug (Allopurinol) and concomitant therapy (Candesartan) that are available as generic. The PI is proposing to study the effects of Allopurinol under FDA-approved indications, which is approved for use in children and adults for the reduction of high uric acid levels. Candesartan is approved for use in children and adults for the reduction of high blood pressure. The concomitant therapy, Candesartan, is required in this protocol to reduce drug-drug interactions with Allopurinol. The medications Lisinopril, Enalapril, and Benazepril are commonly prescribed for hypertension but increase the risk of moderate to severe adverse reactions when used concomitantly with Allopurinol. Losartan is also a blood pressure lowering medication that uniquely lowers uric acid levels which could affect the results of the trial, but does not interact with Allopurinol so will be converted for a different and specific reason. Any participant in the trial who is prescribed Lisinopril, Enalapril, Benazepril, or Losartan at the time of randomization will be converted to a similar or same class of blood pressure lowering medication, Candesartan, which does not interact with Allopurinol or lower uric acid levels. Approximately 1/4 of participants in this trial will qualify for the Candesartan conversion. Candesartan will be supplied by the investigational pharmacy at no cost to participants. Allopurinol will also be supplied by the investigational pharmacy to the treatment group participants.

[figure not shown]
Recruitment and pre-trial medication adjustments:

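### Table 1 reserves no control biomarker samples at Visit 2, although Aim 2 compares 3-month biomarkers with controls; its adverse event coding also needs reconciling with the safety plan

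*Combined protocol and SAP*

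**What the plan says.** **Biomarkers.** The Specific Aims state that the Aim 2 biomarkers "will be collected at 3 and 6 months and compared to baseline of cohorts A and B treatment and control groups". Section 2.1 expects that, after 3 and 6 months, "the biomarker levels will be reduced from baseline in both treated cohort groups compared to control participants". Section 2.2 says "We will measure the following biomarkers from reserved serum and urine samples at the baseline, 3, and 6 month visits". Section 1.2 describes serum and urine collection at baseline, 3 and 6 months and adds "The residual serum and urine samples will be bio-banked for the analyses of Aim 2". The only arm restriction in that sampling text concerns the extra sample at V1A, which is for the treated arm.

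Section 2.3 says that Aim 2 will be analysed in a similar way to Aim 1. The Aim 1 analyses in section 1.3 include this: "Repeated measures ANOVA models will be used to inform from all three time points".

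Table 1 uses letter codes. E is the reservation of residual samples for biomarkers. The row "Data Collection of Control group" reads C (identification), A-E (V1), no visit (V1A), C (V2), A-E (V3). The treated row reads C, G; A-E, G; D, F; C, E, F; A-F.

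**Adverse events.** The only code that mentions them is "F: Pill count, Adherence visual analogue scale, Evaluation of adverse events". The text of section 1.2 says "Adverse events will be collected and adherence will be measured at the V1A, V2, and V3 visits", by means that include a pill count. The Data and Safety Monitoring Plan calls for adverse events to be reviewed with participants at every study visit, with no arm restriction. It defines an adverse event for any subject taking part.

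**The concern.** A visit schedule is what site staff are likely to work from. Code E is missing from one control cell, and that cell is the 3-month visit that Aim 2 depends on. If the table is followed, leftover control serum and urine from that visit are not kept, and they cannot be recovered later. The 3-month comparison of treated with control participants would have no control data. Any three-time-point model for a biomarker would have an empty control cell at month 3.

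The adverse event coding raises a smaller question of the same kind. The table ties adverse event evaluation to pill count and the adherence scale, which make sense only for participants taking Allopurinol. As a result it schedules the evaluation for no control and for nobody at V1. The safety plan schedules it for everyone at each visit.

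**Working it through.** **Inputs.** Enrolment targets come from Table 2: Allopurinol 19 + 9 = 28, control 7 + 7 = 14, total 42. Codes come from Table 1. Full retention is assumed.

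**Step 1: expand the codes** (A-E means A, B, C, D, E; A-F means A to F).

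| Code | Arm | V1 | V1A | V2 | V3 |
|---|---|---|---|---|---|
| E | Allopurinol | yes | no | yes | yes |
| E | Control | yes | no visit | **no** | yes |
| F | Allopurinol | no | yes | yes | yes |
| F | Control | no | no visit | no | no |

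For the treated arm, code E falls at exactly the three time points named in section 2.2. For controls it misses only V2. Each row has one entry per visit column, so a fault in reading the table is unlikely.

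**Step 2: sample sets reserved at 3 months.**

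| | Table 1 (treated vs control) | Text (treated vs control) |
|---|---|---|
| All | 28 vs 0 | 28 vs 14 |
| Cohort A | 19 vs 0 | 19 vs 7 |
| Cohort B | 9 vs 0 | 9 vs 7 |

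**Step 3: sample sets over all three time points.**

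- Treated, under either reading: 28 × 3 = 84.
- Control under Table 1: 14 × 2 = 28. Control under the text: 14 × 3 = 42.
- Total under Table 1: 84 + 28 = 112. Total under the text: 84 + 42 = 126.
- Lost: 42 − 28 = 14 control sets, which is 14/42 = 33.3% of control sets and 14/126 = 11.1% of all sets.

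**Step 4: what is not touched.** Controls have E at V1 and V3, so the baseline-to-6-month biomarker contrast keeps 28 vs 14. They have C at V2, so the standard laboratory work at 3 months is still done. The primary outcome uses baseline and 6 months and does not depend on code E.

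**Step 5: adverse events, texts side by side.** Table 1 schedules evaluation (code F) at V1A, V2 and V3 for treated participants and never for controls. The safety plan asks for review at each study visit without naming an arm. The section 1.2 sentence names V1A, which controls do not attend, and also pill counts. It can therefore be read as describing the treated arm only, in which case it agrees with Table 1. The firmer mismatch is between Table 1 and the safety plan, and it includes V1 in both arms.

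**The case against.** On biomarkers, the other side can say that controls still give serum and urine at V2 under code C, and that the text banks residual samples without excluding them. What is missing is one letter in one cell, in an exploratory aim. This is correct, and it limits the point: the loss occurs only if staff follow the table rather than the text. It does not remove the conflict, because section 2.1 names 3 months in a comparison with controls.

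A reader might infer that the repeated measures analysis of Aim 2 would lose every control. The documents do not support this. Section 2.3 promises only similar analyses, which does not commit every biomarker to the three-time-point model. All controls would drop out only under a complete-case fit, and the plan does not say how missing values are handled.

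A reader might also infer that adverse events in controls would go uncollected, or that the Independent Monitor's report would be biased by unequal ascertainment. The documents do not support that either:

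- The safety plan's rule of review at each visit already covers controls.
- Subjects are asked to telephone about the moderate events it lists.
- Side effects of Candesartan conversion, which can apply to any participant, are reported to the study team and the Independent Monitor.
- The V2 purpose row, shared by both arms, includes a safety check.
- The plan says the progress reports use aggregate data for the whole study population. It also mentions a closed report with masked groups, but it does not clearly say that adverse events are shown by arm.

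What stands on adverse events is a mismatch between schedule and safety plan, not a missing procedure.

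**Conclusion.** The biomarker conflict is real and unambiguous. Followed literally, Table 1 leaves 0 of 14 controls with a reserved 3-month sample, and the exploratory 3-month between-group contrast cannot be estimated. The counts assume Table 2 enrolment and full retention. Whether the loss occurs depends on which text staff follow, and the documents do not say which prevails. The point should be fixed because a lost sample cannot be replaced and the correction is very small. It does not threaten the primary analysis.

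The adverse event point is secondary and held with moderate confidence. Table 1 and the safety plan disagree on who is evaluated and when. No conclusion about biased safety reporting follows.

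**What to change.** 1. Add E to the control Visit 2 cell of Table 1. No extra visit or blood draw is needed. The added work is banking residual aliquots for 14 controls and assaying them. Section 2.2 lists 5 serum and 2 urine inflammasome measures and 5 renal injury measures, 12 in all, so this is 14 × 12 = 168 assays, already implied by Aim 2. If the omission was deliberate, the alternative is to limit the control comparison in Aim 2 and sections 2.1 and 2.2 to 6 months.

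2. Give adverse event evaluation its own code, separate from pill count and adherence, and list it for both arms at every visit they attend, including V1. Change the section 1.2 sentence to match, stating that V1A applies to the treated arm only. Relative to Table 1 this adds 14 × 3 = 42 control reviews (V1, V2, V3) and 28 × 1 = 28 treated reviews (V1), all short, at existing visits and already required by the safety plan. Because the trial is open-label, some difference in reporting between arms may remain.
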